"Efficacy of ENTREN-F Program: A psycho-family and multidisciplinary intervention for children from 8 to 12 years old with childhood obesity. A controlled and randomized clinical trial"

Study Protocol

Date of the document: 31/01/2017

Study Protocol

Background

The World Health Organization (WHO, 2016) places childhood obesity as one of the greatest global challenges at the level of public healthcare. The prevalence of childhood overweight and obesity continues to rise in most countries, associated with short-term medical, psychological and social consequences that worsen in the long term (Simmonds, Llewellyn, Owen, & Woolacott, 2016; Twig et al., 2016).

The mechanisms responsible for the etiology of overweight and obesity are complex. In addition, the dynamic process in which behaviors, cognitions and emotional regulation interact with each other, together with biological parameters (i.e. genetic predisposition, energy and/or metabolic expenditure), environmental factors (i.e. eating habits, sedentary lifestyle) (Stice et al., 1999; Speiser et al., 2005), and psychological factors influence the development and maintenance of these problems. A further important psychological correlate of childhood obesity might be found in familial stress. Even though all these factors may be maintaining the problem and are predictors of a better or worse prognosis in childhood obesity interventions, emotional and family variables are still not included in this type of treatments.

Although the scientific community has been trying for some time to develop effective treatments for childhood obesity (Snethen, Broome, Treisman, Castro, & Kelber, 2016; Epstein, Paluch, Roemmich, & Beecher, 2007), there is clear evidence of the difficulty in obtaining moderate results beyond a slight weight loss (Knop et al., 2015; Skjåkødegård et al., 2014).

Recent systematic reviews have described the predictor variables for a treatment to be more effective. Specifically, treatments focused on the promotion of healthy life habits, including family participation and working from behavioral techniques, have been shown to be the most effective (Snethen et al., 2016; Altman & Wilfley, 2015; Wilfley et al., 2007). In this sense, the involvement of the family in the treatment is associated with long-term stable changes compared with other types of interventions (Wilfley et al., 2007; Epstein, Valoski, Wing, & McCurley, 1994).

Another important aspect in childhood obesity interventions is their intensity and duration. In this sense, medium-high intensities and longer durations have been associated with greater efficacy (Whitlock, O'Connor, Williams, Beil, & Lutz, 2010). Specifically, Kitzmann et al.'s (2010) review noted that with an intervention duration of around four months, the results obtained were as effective as with more extensive interventions.

Adherence to treatment is another crucial aspect in the treatment of obesity. There are studies that define which variables predict the drop-out of treatment, such as the bad relationship between parents and the child, the lack of time and motivation, the coincidence with other academic activities, the high level of family stressors, and the distance between the home and the center where the intervention is being carried out (Brennan, Walkley, & Wilks, 2012; Moroshko, 2011; Braet, Jeannin, Mels, Moens, & Van Winckel, 2010; Barlow & Ohlemeyer, 2006).

Other relevant factors that predict greater treatment effectiveness are variables such as age and gender (Moens et al., 2010; Goossens, Braet, Van Vlierberghe, & Mels, 2009), placing adolescence as a more difficult stage in which to achieve changes. Other variables include psychological problems during childhood (Moens et al., 2010; Epstein, Klein, & Wisniewski, 1994) and the degree of parental motivation (Gunnarsdottir et al., 2011; Braet et al., 2010; Moens, Braet, & Van Winckel, 2010; Braet, 2006). Despite taking into account all the previously described variables, the vast majority of treatments have focused on long-term weight reduction as the sole objective of intervention, leaving aside all these psychological and family correlates that maintain the problem.

Objetive

The main objective is to examine the effectiveness of the intervention program 'ENTREN-F' (intervention for children plus family intervention) on anthropometrics, behavior, psychological and family factors, from a multidisciplinary perspective, compared with another group participating in the same program 'ENTREN' (intervention for children without family intervention) and with a control group (usual treatment) among Spanish children with over-weight and obesity. Finally, the second aim was to evaluate whether the changes were maintained 6, 12 and 18 months after the end of the intervention.

Hyphotesis

The specific hypotheses of the present study were as follows: (a) There will be significant differences in the adherence to treatment, being higher in the ENTREN-F group (b) There will be improvements in clinical outcomes regarding the anthropometric variables of the child, the level of physical activity, psychological distress, and eating disorder of the child, after both interventions (ENTREN and ENTREN-F programme), in comparison to control group (d) There will be only improvements in clinical outcomes regarding in the family's healthy life-style, psychological distress of the parents, and the family environment, after the intervention of the ENTREN-F programme. (e) The significant changes produced will remain stable at the 6, 12 and 18-month follow-up in the ENTREN-F group.

Method

Participants and Recruitment Procedure

The sample will be made up of 240 children of 8-12 years old (IMC>P90). The dropout rate is expected to be 20%. The majority of the participants will be recruited through Primary Health Care Services, in collaboration with Pediatrics Area. Another percentage of the sample contacted the program after receiving information from their school or advertising posters.

Participation was voluntary and informed assent and consent was obtained by each participating family. Participants were told that the personal content of session discussions was confidential and should not be discussed outside the sessions.

Participants were randomly assigned to either (a) the psychofamily-based workshop program (ENTREN-F), (b) the only psychological workshop program (ENTREN) or (c) the Control Group. Participants were asked to complete questionnaires at baseline prior to the intervention (T_0) , at the end of the intervention and (T_1) , at 6-month follow-up (T_2) , at 12-month follow-up (T_3) and at 18-month follow-up (T_4) .

Design and contents

ENTREN Programme (experimental)

This intervention consists in a total of 12 biweekly sessions: 9 sessions of 2-hr only for children, with a further three 3-hr sessions attended by both families and children together: nutrition, physical activity sessions, and a closing event session. Los contenidos

de las sesiones con los niños se basan en una perspectiva cognitivo-conductual e incluyen estrategias de la entrevista motivacional. El objetivo de las sesiones con los niños es trabajar la conciencia del problema, la motivación al cambio, el concepto de salud, la regulación emocional, las habilidades sociales y autoestima. One 2-hr sesión at 6, 12 and 18-month follow-up was provided to refresh skills, their physical activity, and nutritional behaviours.

ENTREN-F Programme (experimental)

ENTREN-F has the same children's intervention than ENTREN. It has extra 6 2-hr sessions to work on family environment and communication, plus three 2-hr sessions attended by both families and children together. One 2-hr sesión at 6, 12 and 18-month follow-up was provided to refresh skills, their physical activity, and nutritional behaviours.

Control Group Programme

The intervention of this group consists in usual treatment in Primary Care provided by Endocrinology Services. 3 monthly face-to-face consultations and continous online monitoring are provided to these families, oriented to promote healthy habits of nutrition and physical activity for 6 months. It works from an exclusively behavioral perspective. We used a *token economy*, a system of contingency management based on the systematic reinforcement of target behavior.

Instruments

• Anthropometric variables

Nurses measured children and parents: height, weight, waist circumference and middle arm circumference. Mother and children's Body mass index (BMI) has been calculated. Participating children's BMI Z-scores was calculated according to the age and specific sex, according to the median and standard deviation, based on the data collected in the Growth Tables of Orbegozo Foundation (Sobradillo et al., 2004).

• Lifestyle habits

Actigraph, model GT3X. The Actigraph (Actigraph TM, LLC, Fort Walton Beach, FL, EE.UU) is a small and lightweight triaxial activity monitor/accelerometer (4,6 x 3,3 x 1,5

cm, 19 g) designed to detect accelerations ranging in magnitude from -6 a 6 g with a frequency response of 0.25–2.50 Hz. Accelerometers were programmed before handing them over to the participants and the data were recorded at a frequency of 30 Hz and reinstated to a period of 60 seconds (epoch) for analysis. The accelerometers were attached to an elastic band and rested on the child's back. They were worn during 7 consecutive days and were only removed for water activities and sleeping. The data were downloaded and analyzed with an Actilife software (v.6.62. Actigraph TM, Pensacola, FL, USA). Level of sedentarity, light, moderated and vogorus activity (min/day) was used.

• Child Emotional Well-being and Eating Pathology

Clinical and standardised diagnostic interview: The Schedule for Affective Disorders and Schizophrenia for School-Age Children- Present and Lifetime version (K-SADS-PL) (Kaufman et al., 1997; De la Peña et al., 2002) is a semi-structured interview which generates DSM-IV Axis I child psychiatric diagnoses. It includes both a screening interview and supplementary questions that are administered to ascertain a diagnosis if deemed relevant. Questions were directed at the children and responses confirmed with the parents. The Spanish version of the interview (De la Peña et al., 2002) was used and the diagnoses were subsequently adapted to the DSM-5 criteria by researchers.

Depressive symptomatology (CDI; 1992; Davanzo & col, 2004): The Child Depression Inventory (CDI) (Kovacs, 2004) consists of 27 items with three response options (0 to 2). Item example: "I am always sad" or I do not like how I am". The total score of the scale ranges from 0 to 54. The internal reliability of the Spanish version was 0.69 (Davanzo, 2004). In the current sample, Cronbach's alpha was 0.68.

Anxiety (SCAS; Spence, 1997; Bermúdez-Ornelas et al., 2010). The Spence Children Anxiety Scale is a 44 items- questionnaire related to anxiety symptoms with four Likert-type options: never (0), sometimes (1), many times (2) and always (3). It also includes 6 positive fill-in items to counteract the negative bias of the previous ones, and whose qualification is not qualified or taken into account in the analyzes. It is calibrated by the sum of the points obtained for each item. The higher the score, the more anxiety. To achieve the Spanish version, the traditional translation-retranslation procedure was used. Psychometric analyses reinforce the construct validity of this scale and show an acceptable internal consistency.

Perfectionism (CAPS; Flett et al., 2000; Castro et al., 2004). The Child and Adolescent Perfectionism Scale (CAPS) consists of 22 items that are answered on a 5-point scale, where 1 is equal to true and 5 is equal to false. It consists of two scales: Self-directed Perfectionism and Socially Pre-Written Perfectionism. In its initial validation the questionnaire reported adequate indices of internal consistency and test-retest reliability ($\alpha = 0.81$, r = 0.74). Similarly, with respect to the Spanish version, Castro et al. (2004) reported on internal consistency indices, Cronbach's alpha of 0.87.

Self-esteem (LAWSEQ; Lawrence, 1981; De Gracia, Marcó & Trujano, 2007). LAWSEQ is composed of 16 items with which it evaluates self-esteem in children, excluding content about image and body satisfaction. Each item is evaluated on a dichotomous scale where they should answer with YES or NO. The higher the score, the higher the personal and competence estimation.

Teasing (POTS; Thompson, JK., Cattarin, J., Fowler, B. & Fisher, E., 199; Sánchez-Carracedo et al., 2011). The Perception of Teasing Scale is a questionnaire of 11 items (Spanish version includes only 9 items) in which it is asked about different situations of ridicule and the level of associated discomfort, valued on a Likert scale with 5 options. Adequate internal consistency.

Personality Features (BFQ-NA; Barbaranelli, Caprara y Rabasca, 1998; Del Barrio et al., 2006). It is adapted from the Big Five model of personality for children and adolescents (Awareness, Openness, Extraversion, Kindness, Emotional Instability). It is a brief questionnaire (65 items that are valued using a scale of 5 alternatives). Good psychometric properties.

Child Eating Behaviour (DEBQ-C; Van Strien & Oosterverld, 2008; Baños et al., 2011). The Dutch Eating Behaviour Questionnaire is an effective instrument for the investigation of the alimentary behavior in children. The results indicate that the DEBQ-C showed an acceptable internal coherence (a = 0.70) and the three factors presented good adjustment indices.

Emotional Regulation (TMMS-24; Mayer y Salovey, 1997; Fernández-Berrocal, Extremera, y Ramos, 2004). The Trait Meta-Mood Scale is a trait scale of emotional meta-knowledge. Specifically, it measures the skills with which we can be aware of our own emotions, as well as our ability to regulate them. The Spanish validation can be found in Fernández.-Berrocal et al. (2004). The scale is composed of 24 items that must be scored with a Likert scale of five points (from 1 = Not at all agree, up to 5 = Strongly agree),

which are grouped in the following dimensions: perception, comprehension and regulation of emotions.

Cuestionario de percepción de estilos de crianza (CRPBI-A; Samper, P., Cortés, M. T., Mestre, V., Nácher, M. J., & Tur, A. M., 2006). The Child's Report of Parent Behaviour Inventory is a 52-item self-report questionnaire that allows to assess family discipline perceived by children from 6 to 16 years old in the relation with their mothers and with their fathers. The abbreviated form of 29 items of the questionnaire (CRPBI-A) was adapted to Spanish by Samper et al. (2006). This instrument consists of six scales that evaluate the following 6 styles of parenting practices: communicative, hostile/rejecting, controlling, permissive, overprotective, and negligent. It is suggested that CRPBI-A is an appropriate multidimensional instrument for the evaluation of parenting styles in research and clinical settings.

Adverse Childhood Events (Oliva Delgado, Jiménez Morago, Parra Jiménez, Sánchez Queija, 2008; in process of Spanish validation by ANOBAS group). It is an inventory designed to analyze the relationship between life stress events and adjustment. It consists of a list of 27 negative events related to the influential contexts during school stage (family, school and peer group).

Social stigma (WBIS; Durso & Latner, 2008; in process of validation by ANOBAS group) The Weight Bias Internalization Scale is an 11-item questionnaire that measures weight-related self- stigma. The scale asks participants to rate how much they agree with each statement as it applies to them on a 5-point Likert-type scale and provides scores in only one domain (e.g., "I hate myself for being overweight"). The WBIS has satisfactory internal consistency (α =.90). A higher score in the WBIS indicates a higher level of weight-related self-stigma.

• Primary caregivers

Depression (BDI-II; Beck, Steer & Brown, 1996; Sanz, Perdigón & Vázquez, 2003). The Beck Depression Inventory (BDI-II) (Beck, Steer & Brown, 1996). It contains 21 items measuring somatic and cognitive--affective symptoms. Higher scores indicate higher levels of depression. The BDI-II has demonstrated high internal consistency in its Spanish version (Sanz, Perdigón & Vázquez, 2003) ($\alpha = 0.87$); in the current study, it was higher ($\alpha = .92$).

Personality Features (NEO Five-Factor [MRH2] Inventory - NEO-FFI; Scandell, 2000) is a shortened version of a solid empirically-validated NEO Personality Inventory-Revised, an implementation of the five-factor model (FFM) of personality.

Eating Behaviour (DEBQ; Van Strien, Frijters, Bergers & Defares, 1986; Cebolla et al., 2014). The Dutch Eating Behaviour Questionnaire includes 3 factors: emotional eating, external eating and restriction.

Emotional Regulation (TMMS-24; Mayer & Salovey, 1997; Fernández-Berrocal, Extremera & Ramos, 2004). The Trait Meta-Mood Scale is used to evaluate the perceived emotional intelligence. The TMMS-24 (Spanish Modified Version of the Trait Meta-Mood Scale) is a trait scale of emotional meta-knowledge. Specifically, it measures the skills with which we can be aware of our own emotions, as well as our ability to regulate them. The Spanish validation can be found in Fernández.-Berrocal et al. (2004). The scale is composed of 24 items that must be scored with a Likert scale of five points (from 1 = Not at all agree, up to 5 =Strongly agree), which are grouped in the following dimensions: perception, comprehension and regulation of emotions.

Child Feeding Questionnaire (CFQ; Birch, Fisher, Grimm-Thomas, Markey & Sawyer, 2001). It includes the scales of supervision, restriction, restriction as discipline and pressure to eat.

Expressed Emotion in family environment (FQ; Wiedemann, Rayki, Feistein, & Hahlweg, 2002; Sepúlveda et al., 2014). The Family Questionnaire was used to assess level of expressed emotion. It contains two scales, critical comments (CC) and emotional overinvolvement (EOI). For Cronbach's alpha for the CC subscale was 0.83 and 0.72 for the EOI subscale for Spanish version (Sepulveda et al., 2014). For the current study, coefficients were slightly higher (CC α = .85 and EOI, α = .76).

Family Environment (HES; Gatshall et al., 2008; Sepulveda et al., 2016). This is an obesogenic environment assessment questionnaire has 10 scales that assess the availability and accessibility of food and physical activity. To calculate the score of a scale, parents had to answer at least 75% of the items. All scales showed adequate internal consistency (α

= 0.66 to 0.84).

Escala eventos estresantes (SRRS; Holmes y Rahe, 1967). The Holmes and Rahe stress scale is a list of 43 stressful life events that can contribute to illness. Adults indicate on a dichotomous scale whether or not the different events have occurred.

Motivation to change in aspects related to obesity (design and validation of the instrument by ANOBAS group).

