## **Statistical Analysis Plan (SAP)**

The statistical considerations for analyzing the data collected in the study are detailed below:

First, analyses will be carried out with the SPSS 26.0 version (IBM, SPSS, 2019).

Descriptive statistics (means, standard deviations, and percentages) of all the sociodemographic, clinical, and psychological variables will be calculated. A Shapiro–Wilk test will be used to check normal distribution.

Participant BMI changes over time by group will be measured using a Kruskal-Wallis test.

To carry out the comparisons, two-way analysis of covariance (ENTREN-F, ENTREN, Control Group) and time (T0,T1, T2 and T3) will be used.

Mixed model repeated measures analyses of covariance models tested whether intervention effects varied for each type of group.

In those cases in which we found significance in the global comparisons, we will carried out pairwise comparisons following asignificant main effect of time (post hoc Bonferroni test).

Finally, the effect size will be measured using partial eta squared ( $\eta$ 2), which estimates the degree of association for the sample. The guidelines for interpreting this value are as follows:  $\geq$ 0.14, large effect;  $\geq$ 0.06, medium effect;  $\geq$ 0.01, small effect (Cohen, 1988). The value P<0.05 was considered as a significant difference.

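### Which outcomes get a follow-up contrast depends on significance: hypothesis (e) is narrower than the second aim, and the SAP's pairwise tests sit behind a global test

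*Protocol*

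**What the plan says.** - Protocol, Objective section: "the second aim was to evaluate whether the changes were maintained 6, 12 and 18 months after the end of the intervention". The aim is not limited to significant changes or to one arm.
- Protocol, Hypothesis section, item (e): "The significant changes produced will remain stable at the 6, 12 and 18-month follow-up in the ENTREN-F group". This limits the maintenance question to changes that were significant, in one arm.
- Protocol, Participants and Recruitment Procedure: questionnaires run from T0 to T4, with the last two "at 12-month follow-up (T_3) and at 18-month follow-up (T_4)".
- SAP: a group-by-time analysis of covariance and a repeated-measures mixed model, with a time factor of T0, T1, T2 and T3. T4 is not listed.
- SAP, post hoc comparisons: these are made "In those cases in which we found significance in the global comparisons". The same sentence ties them to a significant main effect of time, with Bonferroni correction. The threshold is "The value P<0.05 was considered as a significant difference".

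The SAP text available for review describes no separate maintenance analysis and no estimate at follow-up that is reported regardless of a test result. It does plan descriptive statistics for all variables.

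**The concern.** If outcomes reach the follow-up question because a test on the same data was significant, two things go wrong. The outcomes let through are partly those on which chance was favourable, so their effects are overstated. Real effects that miss the threshold are left without a visit-specific contrast, so a reader cannot tell an absent effect from an unreported one.

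The second aim is then answered on a data-selected subset. The pool is large: the protocol lists many child and caregiver scales, and no primary endpoint is named. Small effects are plausible, since the protocol's Background itself describes the difficulty of getting beyond slight weight loss.

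This point is about which outcomes are followed up. How stability should be tested is a different question.

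**Working it through.** **Inputs from the documents.** "The sample will be made up of 240 children of 8-12 years old"; "The dropout rate is expected to be 20"%; three arms; threshold 0.05. The documents give no figure for maintenance or selection, so there is none to reproduce.

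**Assumptions.** Equal allocation (the ratio is not stated), so 240 × 0.8 / 3 = 64 per arm; two-sided testing; SD of 1; equal correlation r between visits, varied over a range. BMI change has its own rank test in the SAP, so the figures describe outcomes analysed with the model.

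**1. The gate the SAP states: a global test over T0 to T3.** Trials were simulated with 64 per arm and an effect d in ENTREN-F from T1 onward, fully kept, with none in the other arms. The group-by-time F test has (3−1)(4−1) = 6 and 3 × 63 × 3 = 567 degrees of freedom.

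Mean estimated ENTREN-F effect in trials that pass, for true d = 0.2:

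| r | Mean estimate | Overstatement |
|---|---|---|
| 0.5 | about 0.33 | 0.33/0.20 − 1 = 65% |
| 0.8 | about 0.26 | 0.26/0.20 − 1 = 30% |

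At r=0.5 the estimates at T1, T2 and T3 were about 0.34, 0.32 and 0.34. The excess is about equal at every visit, because the global test does not favour T1.

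Share of trials that pass, for true d = 0.3:

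| r | Pass | No pairwise contrast |
|---|---|---|
| 0.5 | about 37% | 63% |
| 0.7 | about 61% | 39% |
| 0.8 | about 82% | 18% |

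**2. If the gate is the main effect of time.** The SAP wording allows this reading. That effect averages over arms, so a benefit confined to one arm is diluted. With equal arms it is independent of the between-arm contrasts, so it inflates within-arm changes but not between-arm differences.

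**3. Effects that appear only at T2 and T3.** For 0.3 SD in ENTREN-F alone, the group-by-time test is significant in about 50% to 92% of trials for r from 0.5 to 0.8. A main-effect-of-time gate opens in about 35%, 55% and 75% at r=0.5, 0.7 and 0.8. Late effects at 6 and 12 months therefore do enter the global test. T4 enters no planned model.

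**4. Hypothesis (e) taken literally: follow an outcome only if its T0–T1 change had P<0.05.** For a within-arm change d:

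- SE = √(2(1−r)/64) and θ = d/SE
- mean T1 change given significance = d + SE × φ(1.96−θ)/(1−Φ(1.96−θ))
- mean T2 change given selection = d + 0.5 × (T1 excess), because two changes from a shared baseline correlate 0.5 under equal visit correlation

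For d = 0.2 and r = 0.5: SE = √(1/64) = 0.125 and θ = 1.6, giving T1 = 0.330. T2 = 0.2 + 0.5 × 0.130 = 0.265. Apparent loss = (0.330 − 0.265)/0.330 = 20%, although nothing was lost.

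| r | T1 given significance | Apparent loss at T2 |
|---|---|---|
| 0.5 | 0.33 | 20% |
| 0.7 | 0.27 | 13% |
| 0.8 | 0.24 | 8% |

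For d = 0.5 the apparent loss is below 1% at each of these correlations.

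**The case against.** Hypothesis (e) is a prediction, not an analysis rule. The second aim has no significance filter, the SAP's models are not conditioned on T1, and running post hoc tests only after a significant overall test is ordinary practice. Descriptive means and SDs are also planned for all variables. All of this is fair, and it rules out two stronger conclusions that a reader might draw.

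- *A maintained benefit will look like partial relapse.* The SAP's gate does not produce this, since it inflates T1, T2 and T3 about equally. The artefact needs selection on the T1 result, which the SAP does not state and which comes only from a literal reading of hypothesis (e). Even then it is confined to small effects.
- *Effects that appear later are never tested.* T2 and T3 are in the time factor, so late effects at 6 and 12 months are tested globally. The 18-month visit goes untested because T4 was left out of that factor, which is a separate omission.

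What remains is that hypothesis (e) and the second aim do not ask the same question, and that the plan conditions its visit-specific comparisons on significance. Descriptive means by themselves do not supply adjusted arm differences with intervals.

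**Conclusion.** The point holds in limited form. Hypothesis (e) is narrower than the second aim, and the SAP's gating makes the set of outcomes with a follow-up contrast depend on the data.

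The consequence is material for true effects of about 0.2 to 0.3 SD. Passing a group-by-time gate overstates a 0.2 SD effect by roughly 30% to 65% at all visits, and 18% to 63% of trials with a real 0.3 SD effect would yield no pairwise result. The spurious loss of 8% to 20% is conditional on the literal reading of hypothesis (e). At 0.5 SD or more the bias is negligible.

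All sizes rest on 64 per arm, equal visit correlation of 0.5 to 0.8, and an effect in one arm only. The mismatch in wording and the absence of T4 from the SAP time factor need no assumption.

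**What to change.** 1. Delete the word significant from hypothesis (e), so that it matches the second aim.
2. Add T4 to the SAP time factor.
3. For every outcome in hypotheses (b) and (d), report baseline-adjusted ENTREN-F minus control and ENTREN-F minus ENTREN differences with 95% CI at T1, T2, T3 and T4, whatever the T1 or global test result.
4. Base the maintenance statement on those estimates.

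The cost is a change of wording in the protocol and SAP and more rows in the results table. No extra data are needed, because T4 is already scheduled. The drawback is that many ungated intervals will be shown, so the SAP should say that they are to be read as estimates and not as confirmatory tests.

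### Hypotheses (d) 'only' and (e) 'remain stable' are tied to no analysis that can answer them: the post hoc rule compares time points, no ENTREN-F versus ENTREN contrast is named, and T4 is not listed

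*Protocol*

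**What the plan says.** **Protocol, hypotheses.** Hypothesis (d): "There will be only improvements in clinical outcomes regarding in the family's healthy life-style, psychological distress of the parents, and the family environment", after ENTREN-F. Hypothesis (e): "The significant changes produced will remain stable at the 6, 12 and 18-month follow-up in the ENTREN-F group". Hypothesis (b), on the child outcomes, is explicitly comparative: "after both interventions (ENTREN and ENTREN-F programme), in comparison to control group". Neither (d) nor (e) carries such a phrase.

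**Protocol, objective.** ENTREN-F is to be "compared with another group participating in the same program 'ENTREN' (intervention for children without family intervention) and with a control group (usual treatment"), and family factors are among the outcomes. Maintenance at 6, 12 and 18 months is the second aim.

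**Protocol, participants.** "The sample will be made up of 240 children of 8-12 years old (IMC>P90"). "The dropout rate is expected to be 20" per cent. Assessments run from T0 to T4, and T4 is the 18-month visit.

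**SAP.** The plan has four elements:
- a Kruskal-Wallis test of BMI change by group;
- a two-way analysis of covariance with the three groups and time T0 to T3;
- a mixed repeated-measures model of whether intervention effects vary by group, with no visits listed;
- after a significant global result, "pairwise comparisons following asignificant main effect of time (post hoc Bonferroni test").

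Significance is P<0.05. The SAP does not define 'stable', gives no margin or confidence-interval rule, and does not say which test answers which hypothesis.

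**The concern.** Hypothesis (e) is a claim of no change in one arm. A test built to detect a difference cannot establish it, because a non-significant result may only reflect low power. A Bonferroni adjustment makes non-significance easier to obtain. If (e) were read that way, a smaller sample or more dropout would make maintenance easier to report.

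Hypothesis (d) makes two claims: that ENTREN-F improves family outcomes, and that the other arms do not. The first needs a direct comparison between arms. The second cannot be shown by a difference test. If (d) were read from a significant change in ENTREN-F beside a non-significant one in ENTREN, chance alone could produce that pattern when the two arms benefit equally.

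At stake are the second aim of the trial and the distinctive claim for the family module.

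**Working it through.** **1. Which listed analysis could answer each hypothesis?**

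| Analysis in the SAP | (d) ENTREN-F only | (e) stable in ENTREN-F to 18 months |
|---|---|---|
| Kruskal-Wallis | BMI only, not family outcomes | does not address stability in one arm |
| Group and time ANCOVA | three-group test, no pair of arms named | T0–T3 only |
| Mixed model | shows whether effects vary, not which arms differ | compares arms, not T1 with follow-up in one arm |
| Bonferroni pairs after the main effect of time | compares visits, not arms | pools the arms, or is a difference test if run within arm |

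The 18-month part of (e) appears in no listed analysis.

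**2. Inputs for the size.** The sample of 240 cannot be reproduced, because no effect size, SD, power or allocation ratio is given. Assuming 1:1:1 allocation, 240/3 = 80 per arm, and 80 × 0.8 = 64 completers. Further assumptions: a gain of 0.3 SD at T1, correlation ρ between visits of 0.6–0.8, two-sided tests, and four visits giving six pairs, so α = 0.05/6 = 0.0083.

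**3. Power to see relapse within ENTREN-F.** This is a paired t-test with SD of change √(2(1−ρ)) and non-centrality loss × √64 / √(2(1−ρ)). For a loss of 0.15 SD (half the gain), power is 0.091 / 0.129 / 0.214 at ρ = 0.6 / 0.7 / 0.8, so the loss is missed 91% / 87% / 79% of the time. For a loss of 0.30 SD (the whole gain), power is 0.488 / 0.646 / 0.853, so it is missed 51% / 35% / 15% of the time.

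**4. Conditioning on what (e) says.** The hypothesis concerns changes that were significant. T0, T1 and one follow-up visit were simulated with equal correlations, keeping only trials with a significant T0–T1 gain (accurate to about one percentage point):

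| True loss by follow-up | T1 versus follow-up not significant | and follow-up still significantly better than T0 |
|---|---|---|
| Half the gain | about 76–84% | about 15–23% |
| All of the gain | about 11–35% | under 1% |

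**5. Sensitivity to a larger gain.** With an assumed 0.5 SD gain, no conditioning and six pairs, losing half (0.25 SD) is missed 76% / 55% / 33% of the time at ρ = 0.5 / 0.7 / 0.8. Losing all of it is missed 11% / 1% at ρ = 0.5 / 0.7.

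**6. Hypothesis (d).** If two independent arms have the same true benefit and each within-arm test has power p, then P(ENTREN-F significant, ENTREN not) = p(1−p). At p = 0.5 this is 0.25, the maximum; at p = 0.3 or 0.7 it is 0.21. For a 0.5 SD benefit at α = 0.0083 it falls to 9% (ρ = 0.5) or 1% (ρ = 0.7). A direct two-sided 0.05 contrast would wrongly favour ENTREN-F in 0.05/2 = 2.5% of cases per outcome.

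**The case against.** A reader might infer that the plan will decide (d) and (e) by non-significant within-arm comparisons. The documents do not say so. A main effect of time pools the arms on its plain reading, so a within-arm use is an inference. The SAP also plans a group-and-time ANCOVA and a mixed model of whether effects vary by group, and the main objective compares ENTREN-F with both other arms. Used for (d), the group-by-time test would not carry the error in step 6. This part of the objection stands: the risk is what the plan permits, not what it prescribes.

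A reader might also infer that complete relapse could readily be reported as success. That largely fails. The same six pairs include T0 versus each follow-up visit, and requiring follow-up to beat baseline cuts the undetected share to under 1%. With a 0.5 SD gain, full relapse is mostly detected even without that check.

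Finally, superiority over control at follow-up is not stability. An arm can lose half its gain and still beat control, or keep all of it and fail if control improves too. This also stands, and it limits what the between-arm differences can be said to show.

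The objection does not remove the gap itself. A three-group test does not identify ENTREN-F versus ENTREN, none of the planned models tests retention within ENTREN-F, and T4 is not listed.

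**Conclusion.** The concern holds in a limited form. As written, the SAP does not answer 'remain stable' in (e) or 'only' in (d), and it lists no analysis at 18 months. If a non-significant T1-to-follow-up difference were taken as maintenance, loss of half of a significant 0.3 SD gain would pass in about 76–84% of cases. With the added requirement that follow-up beats baseline, about 15–23% would still pass. The point about partial relapse therefore survives; the point about full relapse largely does not. For (d), the false pattern under equal benefit is at most 25%, and only if the planned between-group test is set aside.

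Equal allocation, the size of the gain, the visit correlations, two-sided testing and the number of pairs are assumptions, because the documents give none of them. The gap in the mapping from hypotheses to tests does not depend on them. This should be corrected before analysis.

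**What to change.** 1. Base the post hoc comparisons on the group-by-time interaction instead of the main effect of time, and add T4 to the model.
2. Decide (d) by the baseline-adjusted ENTREN-F minus ENTREN and ENTREN-F minus control differences at T1 on the family outcomes (HES, BDI-II, FQ), each with a 95% CI. Drop 'only' from the hypothesis.
3. For (e), report the baseline-adjusted ENTREN-F minus control and ENTREN-F minus ENTREN differences at T2, T3 and T4 with 95% CIs, labelled as evidence of sustained benefit and not of stability.
4. Also for (e), report the ENTREN-F change from T1 and from T0 to each follow-up visit with 95% CIs. State that a non-significant change from T1 is not evidence of stability.

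The cost is a rewording of two hypotheses and a short list of contrasts in the SAP. No new data are needed, since T4 is already collected. The downside is that maintenance and exclusivity become harder to claim.

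A formal claim of stability would need a justified margin as well. As an illustration, a 0.25 SD margin (one-sided 0.025, 80% power, no true loss) needs n = 2(1−ρ)(1.96 + 0.84)²/0.25², which is 126 / 76 / 51 completers in the arm at ρ = 0.5 / 0.7 / 0.8, against about 64 expected.
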